## **4.3 SAFETY REVIEWS, STOPPING CRITERIA, AND COMMUNICATION PLAN**

Periodic safety reviews, including reviews of treatment-emergent AEs (TEAEs) that meet the Stopping Criteria, will be performed by the unblinded, independent SMC (Section 13.1) throughout the study, as specified below. The study can be terminated at any time based on the findings of any safety reviews.

### **4.3.1 Safety Monitoring Committee Reviews**

The independent SMC will review unblinded, aggregate safety data periodically and will review SAE reports in real time. Recommendations based on these reviews will be provided to the Sponsor.

The SMC will also review SAEs that occur in the sentinel patients (Section 4.3.2) and TEAEs that meet the Stopping Criteria (Section 4.3.4). In addition, the SMC will review the Dose Escalation Committee's decisions regarding dose escalation and continuation to multiple dosing, and the chairperson will endorse the decision. Neither escalation to the next dose level nor continuation to multiple dosing may proceed without review of unblinded data by the SMC and subsequent endorsement by the committee Chair.

Based on any of the safety reviews performed by the SMC, the SMC may recommend stopping the study at any time.

### **4.3.2 Safety Review After Sentinel Patients**

The SMC will perform reviews of any SAEs that occur in the sentinel patients. If either of the sentinel patients in a cohort experiences an SAE within 48 hours postdose, all pertinent safety data will be provided to the SMC. No further patients in the cohort will be dosed pending this data review. The SMC will determine if it is safe to proceed with the cohort, or, in conjunction with the Dose Escalation Committee, whether an intermediate dose should be selected for the remaining patients in that cohort.

### **4.3.3 Dose Escalation and Continuation to Multiple Dosing**

The Dose Escalation Committee will review blinded data to make the decision regarding escalation to each subsequent dose and whether a single dose cohort can proceed to multiple dosing. After all patients in the 2, 4, 8, and 16 mg cohorts complete the Day 28 Visit and all patients in the 32 mg cohort complete the Day 14 Visit, the Dose Escalation Committee will review:

- Safety data from all patients in the current cohort through the Day 28 visit (2, 4, 8, and 16 mg cohorts) or Day 14 (32 mg cohort).
- Any available safety data from patients in the current cohort through the Day 56 visit (2, 4, 8, and 16 mg cohorts) or Day 28 visit (32 mg cohort).
- Any available safety data from all other cohorts, including those that have proceeded to multiple dosing (for the 4, 8, 16, and 32 mg dose cohorts, a minimum of 50% of patients in the previous cohort must have received at least 2 doses in the multiple dose phase, and all

data from the single-dose phase must be reviewed for the current cohort to proceed to multiple doses).

- Treatment-emergent adverse events (TEAEs) that resulted in stopping criteria review (Section 4.3.4).

The Dose Escalation Committee may decide to enroll a larger number of patients in a cohort if further information is needed regarding single administration at that dose, provided no suspected unexpected serious adverse reactions (SUSARs) have occurred at that dose. For the next cohort, the Dose Escalation Committee may decide to select an intermediate dose, extend the current dose level, or select a higher dose. The high dose of 32 mg will not be exceeded; if the Sponsor decides that doses >32 mg should be explored, this will be addressed in a protocol amendment.

If the Dose Escalation Committee determines that the cohort should not continue to multiple dosing, that cohort will end. Patients will be monitored for safety through 8 weeks postdose. The Dose Escalation Committee may identify a lower dose for the subsequent cohort.

All recommendations will be reviewed by the SMC and endorsed by the chairperson. Neither escalation to the next dose level nor continuation to multiple dosing may proceed without review of unblinded data by the SMC and subsequent endorsement by the committee Chair. Sites will be notified rapidly of any decisions made.

#### **4.3.4 Stopping Criteria**

##### **4.3.4.1 Single-dose Phase**

During the single-dose, dose escalation phase, dosing will be suspended:

1. If a single patient experiences an SAE assessed as related to study drug;
2. If  $\geq 2$  patients experience a TEAE of  $\geq$ Grade 3 (using National Cancer Institute Common Terminology Criteria for AE [NCI CTCAE] grading) that is assessed as related to study drug; or
3. If  $\geq 4$  patients experience a non-serious TEAE of  $\geq$ Grade 2 within the Medical Dictionary for Regulatory Activities (MedDRA) High Level Group Term (HLGT) *Spinal cord and nerve root disorders*, assessed as related to study drug.

Objective stopping criterion (#3) was developed to assess any potential events of neurological toxicity that were not otherwise captured via surveillance of serious and severe TEAEs as outlined in criteria 1 and 2. Certain adverse events may be due to the IT administration and are therefore exempt from the stopping criteria (discussed below).

If the stopping criteria are met, the unblinded safety data will be reviewed in a timely manner by the SMC to determine if it is safe to proceed with the cohort or if an intermediate dose should be selected for the remaining patients in that cohort. If a determination is made to resume the study, information will be submitted to the regulatory authorities in accordance with local regulations (eg, amendment) prior to restarting treatment.

Any SUSARs that occur will be reported to regulatory authorities as required. If a decision is made to terminate dosing in a cohort, all Investigators will be informed immediately, as detailed in [Section 4.3.5](#).

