#### Dose Escalation Committee Review

The decision regarding escalation to each subsequent dose and whether a single dose can proceed to multiple dosing will be made by the Dose Escalation Committee. The Dose Escalation Committee will be blinded to treatment assignment throughout the study. All recommendations of this committee will be reviewed by the Safety Monitoring Committee (SMC) and endorsed by the chairperson.

Safety Monitoring Committee Review: Throughout the study, unblinded aggregate safety data will be reviewed periodically and on an ad hoc basis by the SMC. The SMC will review any SAEs that occur in sentinel patients in order to determine if the cohort should continue or if a lower dose should be selected. In addition, if treatment-emergent adverse events (TEAEs) occur that meet the Stopping Criteria, the SMC will review the unblinded safety data and determine whether it is safe to proceed with the cohort.

Stopping Criteria: During the single-dose, dose escalation phase, dosing will be suspended:

1. If a single patient experiences an SAE assessed as related to study drug;
2. If  $\geq 2$  patients experience a TEAE of  $\geq$  Grade 3 (using National Cancer Institute Common Terminology Criteria for AE [NCI CTCAE] grading) that is assessed as related to study drug; or

Sponsor: Wave Life Sciences	Investigational Product: WVE-120101	Phase: 1b/2a	EudraCT Number: 2016-005095-10

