
3. If <math>\geq 4</math> patients experience a non-serious TEAE of <math>\geq</math>Grade 2 within the Medical Dictionary for Regulatory Activities (MedDRA) High Level Group Term (HLGT) Spinal cord and nerve root disorders, assessed as related to study drug.
 
Adverse event (AE) terms related to lumbar puncture and administration (eg, procedural pain, traumatic lumbar puncture, or post-lumbar puncture syndrome) will be exempted from the assessment of Stopping Criteria. A full list of AE terms exempt from the Stopping Criteria is provided in Table 4 in Section 4.3.4.1.
 
If a determination is made to resume the study, information will be submitted to the regulatory authorities in accordance with local regulations prior to restarting treatment.
 
During the multiple-dose phase, dosing will be stopped for an individual patient if:
 
 
1. Patient experiences a serious or intolerable adverse event (AE), that in the Investigator’s opinion requires study drug discontinuation.
 
2. Patient experiences the same related TEAE <math>\geq</math>Grade 3 twice (excepting exempt TEAEs noted in Table 4).
 
 
If a patient meets the individual stopping criteria in the multiple-dose phase, that patient will not receive any more doses of WVE-120101. The patient will be followed up for safety per protocol.
			

Number of Patients: Approximately 60 patients will be enrolled.
			

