#### 4.1.4 Multiple-Dose Phase

The Dose Escalation Committee will determine if a dose cohort can proceed to multiple dosing.

Patients who participated in the single-dose portion of the study must complete the 8-week washout period (2, 4, 8, and 16 mg cohorts) or 4-week follow-up period before receiving additional doses. Patients will visit the clinic on Day 56 (2, 4, 8, and 16 mg cohorts) or Day 28 (32 mg cohort only) for the first of 3 monthly IT doses (Days 56, 84, and 112 or Days 28, 56, and 84) (Table 1 and Table 2).

Patients who are enrolled into the multiple-dose portion of the study only will undergo the Prescreening (Visit 1) and Screening (Visit 2) visits. Patients in the 2, 4, 8, and 16 mg cohorts will not participate in Visits 3 through 7, and will receive their first dose on Visit 8. Patients will return for 2 additional doses (Visit 9 and Visit 10) and for all follow-up visits (Table 3). Patients in the 32 mg cohort will not participate in Visits 3 through 6 and will receive their first dose on Visit 7. Patients will return for two additional doses (Visit 8 and Visit 9) and for all follow-up visits (Table 3).

Within 1 week prior to each lumbar puncture, a blood sample will be tested locally for platelet count and prothrombin time to confirm that it is safe to proceed with the lumbar puncture (Section 8.2.6). Other predose assessments may also be performed up to 1 week prior to dosing, as specifically listed in Table 1, Table 2, and Table 3.

Immediately after study drug administration, all patients should be ambulatory and active for approximately 30 minutes postdose. The Investigator should note any subtle weakness or fatigue during this period. Formal physical examinations targeting the neurological system, will be performed at the time points noted in the Schedule of Assessments (Table 1, Table 2, and Table 3). Any postdose SAEs will be monitored until resolution.

Following each dose, patients will remain in the clinic for a minimum of 4 hours postdose for safety monitoring. In addition, patients will be assessed for safety, PK, PD, and clinical effects.

The SMC will periodically review unblinded, aggregate safety data (Section 4.3.1).

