**4.3.4.2 Multiple-dose Phase Stopping Criteria for an Individual Patient**

Dosing will be stopped for an individual patient if:

1. Patient experiences a serious or intolerable AE that, in the Investigator’s opinion, requires study drug discontinuation.
2. Patient experiences the same related TEAE ≥Grade 3 twice (excepting exempt TEAEs noted in [Table 4](#)).

If a patient meets the individual stopping criteria in the multiple-dose phase, that patient will not receive any more doses of WVE-120101. The patient will be followed up for safety per protocol.

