### 4.3.5 Communication of Emergent Safety Concerns

Enrollment to the study will be closely monitored by the Sponsor. If the stopping criteria are met at any point in the study, enrollment and dosing will be suspended for all cohorts until the data are reviewed. Similarly, if an SAE occurs in the sentinel patients in a cohort, no additional patients will be dosed in that cohort until the safety data are reviewed.

All sites will be informed by fax and email if enrollment and/or dosing is suspended. In addition, if enrollment is suspended, the interactive voice/web response system (IXRS) will be adjusted such that no patients can be randomized to treatment or receive additional doses of study drug until the safety review has been completed and a decision has been made to resume enrollment/dosing.

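### The protocol contradicts itself on whether group stopping criteria 1 to 3 apply during the three repeat doses; read literally, they do not

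*Combined protocol and SAP*

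**What the plan says.** Section 4.3.4.1, headed for the single-dose phase, introduces three group criteria with "During the single-dose, dose escalation phase, dosing will be suspended". They are: one patient with a related SAE; at least 2 patients with a related TEAE of Grade 3 or higher; and at least 4 patients with a related non-serious TEAE of Grade 2 or higher in the MedDRA group for spinal cord and nerve root disorders. The synopsis carries the same phase limit. The section explains the third rule: "Objective stopping criterion (#3) was developed to assess any potential events of neurological toxicity that were not otherwise captured" by the first two.

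For repeat dosing, section 4.3.4.2 begins "Dosing will be stopped for an individual patient if", and the synopsis agrees: "During the multiple-dose phase, dosing will be stopped for an individual patient if". The two triggers are a serious or intolerable AE that the investigator thinks requires discontinuation, and the same related TEAE of Grade 3 or higher twice in one patient.

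Section 4.3.5 reads differently: "If the stopping criteria are met at any point in the study, enrollment and dosing will be suspended for all cohorts", pending data review. It adds that the IXRS will block further doses while enrollment is suspended.

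On oversight, section 4.1.4 says "The SMC will periodically review unblinded, aggregate safety data", and the synopsis says that "unblinded aggregate safety data will be reviewed periodically and on an ad hoc basis by the SMC". Section 4.3.3 ties each cohort's move to multiple dosing to the cohort before it: "a minimum of 50% of patients in the previous cohort must have received at least 2 doses in the multiple dose phase".

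**The concern.** A stopping rule has to tell sites and the SMC which events count. Here one section confines the group criteria to the first dose, and another speaks of the whole study. If the narrow text governs, events that would halt the trial after dose 1 would not halt it after doses 2 to 4. Those are the doses at which any cumulative neurological effect would be expected to show.

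The stated purpose of criterion 3 is to catch neurological toxicity too mild for the serious and severe rules. Nothing in that purpose ends with the first dose. Patients who enter directly at multiple dosing are never in the phase that the criteria name.

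The 32 mg cohort is the most exposed. For lower cohorts, some repeat-dose data must exist before the next cohort may proceed. No cohort follows 32 mg.

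**Working it through.** The documents give no operating characteristics for these rules, so there is no figure to reproduce. The check has two parts.

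**1. The text, event by event**

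| Event during repeat dosing | 4.3.4.1 and synopsis | 4.3.4.2 (individual) | 4.3.5, broad reading |
|---|---|---|---|
| One related SAE | wrong phase | that patient only, if the investigator judges it requires discontinuation | suspends all cohorts |
| Related Grade 3 or higher TEAE in 2 patients, once each | wrong phase | not met by the Grade 3 rule (needs the same event twice in one patient) | suspends all cohorts |
| Related, tolerable, non-serious Grade 2 nerve-root TEAE in 4 patients | wrong phase | not met | suspends all cohorts |

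Section 4.3.5 defines no criteria of its own. It points back to criteria that carry a phase limit, so it cannot settle the question alone.

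**2. The size of the affected period**

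Inputs: 9 active and 3 placebo patients per cohort (6.1); 1 single dose and 3 repeat doses (4.1); the gate of 50% of patients with 2 repeat doses (4.3.3).

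- Active doses per cohort: 9 × 4 = 36. In the multiple-dose phase: 9 × 3 = 27, or 75%. This assumes full roll-over or replacement.
- Repeat doses guaranteed to have been given before the next cohort starts multiple dosing: 6 × 2 = 12 of 12 × 3 = 36, or 33%, plus any other available data. At 32 mg no such gate follows.

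**Chance of a criterion 3 cluster.** Let p be an assumed risk per dose of a qualifying event in an active patient, constant and independent across doses, with no placebo events. The risk per patient over three doses is 1 − (1 − p)³. The number of affected patients is binomial with n = 9, and the rule needs 4.

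| p per dose | At least 4 of 9, first dose | Risk per patient, 3 repeat doses | At least 4 of 9, repeat doses |
|---|---|---|---|
| 5% | 0.1% | 14.3% | 2.9% |
| 10% | 0.8% | 27.1% | 20.7% |
| 20% | 8.6% | 48.8% | 72.2% |
| 30% | 27.0% | 65.7% | 95.1% |

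With a constant risk per dose, a cluster is far more likely in the phase where the rule does not clearly apply.

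**False triggers if criterion 3 is extended.** Let q be an assumed background per puncture of qualifying events wrongly judged drug-related, in all 12 patients, threshold 4, counted per cohort.

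| q | Repeat doses only (3 punctures) | All four punctures |
|---|---|---|
| 2% | 0.4% | 1.1% |
| 5% | 7.9% | 16.8% |
| 10% | 41.7% | 63.7% |

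**The case against.** The strongest reply is that 4.3.5 is operative text. It suspends enrollment and dosing in all cohorts and blocks further doses, and section 4.3 places SMC review of events meeting the criteria throughout the study. On that reading the sponsor already intends what is asked for. A narrower version says that lower cohorts' repeat dosing may overlap the next cohort's single-dose phase, so those events could count as falling within dose escalation. That version runs out once 32 mg single dosing ends.

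Oversight is also real without a numeric rule. The schedules require a neurological examination before each dose, from 30 minutes to 4 hours after it, and at the main follow-up visits. CSF protein, glucose and white cells are checked before every dose. The eCRF has a neurological form with instructions to report worsening. The SMC sees SAE reports in real time, reviews unblinded data periodically and ad hoc, and may recommend stopping at any time. Entry to 32 mg multiple dosing itself needs unblinded SMC review and endorsement by its chair.

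All of this stands, and it limits the point. A reader might infer that a repeat-dose cluster trips no written rule at all. The documents do not support that, because 4.3.5 can be read to cover it. A reader might also infer that 32 mg repeat dosing goes unreviewed. That is not shown either: the SMC charter, which is not among the documents, may set the review dates. What the reply does not remove is the contradiction. If 4.3.5 governs, the limit in 4.3.4.1 and the synopsis is wrong. If 4.3.4.1 governs, 4.3.5 is.

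**Conclusion.** The concern holds as a conflict of scope. Under the literal text of 4.3.4.1, 4.3.4.2 and the synopsis, no group suspension follows from criterion 1, 2 or 3 events during 27 of 36 planned active doses per cohort, or during any dose of a direct entrant. Under 4.3.5 it may.

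Because SAEs are reviewed in real time, the part most dependent on periodic or discretionary review is a set of related, tolerable, non-serious Grade 2 nerve-root events spread over several patients. It matters most at 32 mg. The amendment should be made, but this is not evidence that patients are unprotected.

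The dose counts rest on full roll-over or replacement. Every event rate above is an assumption, since the documents give none, and so is counting per cohort, since the protocol does not state the denominator. Even with the rule in force, a threshold of 4 among 9 active patients is insensitive when few are affected: with 20% of patients affected in a phase, it trips 8.6% of the time. SMC judgement remains the main protection at such rates.

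Nor does the point show that the planned doses are unsafe. Section 1.3 is inconsistent about rat nerve-root findings after repeat dosing, and a reader might be tempted to link the two. No stopping rule rests on that wording.

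**What to change.** In section 4.3.4 and the synopsis, state that criteria 1 to 3 apply in both the single-dose and multiple-dose phases, with their existing thresholds, Table 4 exemptions, suspension of dosing and prompt unblinded SMC review. Keep the individual-patient rules in 4.3.4.2 as an addition. Section 4.3.5 then agrees as it stands.

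Three refinements may look attractive but should be left out.

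- Raising the criterion 3 threshold to 5 if early blinded data suggest a high background. Blinded 9:3 data cannot separate background from drug effect, and at an assumed 20% risk per dose the chance of detection over the repeat doses falls from 72% to 47%.
- Leaving suspension to SMC discretion. This could weaken the automatic suspension that 4.3.5 may already provide.
- Restarting the count at multiple dosing. Three patients in one phase and three others in the next would then trip nothing.

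The change needs a protocol amendment of a few lines, with no new visits, samples or patients. Its cost is some added suspensions and SMC reviews from procedure-related events judged drug-related, since Table 4 exempts bruising, discomfort, pain, headache and puncture terms but no nerve-root terms. Section 4.3.4.1 requires a submission to the regulatory authorities before each restart, so a related SAE in the multiple-dose phase would carry that delay too.

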In single- and repeat-dose toxicity studies conducted in rats and monkeys, IT administration of WVE-120101 was associated with the test-article related, non-adverse finding of transient limb dysfunction in both species. In the single-dose GLP rat study, related findings (splayed limbs, righting reflex impaired, ataxia, or low carriage) were reported at doses of 0.1, 0.25, and 0.4 mg, during the immediate postdose observation period, but resolved completely within 72 hours. The incidence of limb dysfunction increased with increasing dose (15/20 animals in the 0.1 mg group, 31/40 animals in the 0.25 mg group, and 35/40 animals in the 0.4 mg group); however, it was not clear if the findings related to dose or increasing test-article concentration in the CNS. There was a marked decrease in the observation of limb dysfunction or similar neurological findings at the 0.05 mg dose in the repeat-dose study (5/20 animals had transient ataxia after the first dose only; no events of limb dysfunction were reported) and progression of the neurological findings were not observed with repeat dosing. Findings of limb dysfunction were also observed in single- and repeat-dose studies in monkeys. In these monkey studies, limb dysfunction was not observed at the lowest dose (2 mg), and was observed infrequently at the mid-dose (4 mg); the highest incidence was observed in the 6-mg (high dose) group. No other related findings were observed in monkeys. In both species, events of limb dysfunction appeared to be dose- and test article-related, although the transience of the observation and full recovery of animals led to its assessment as a non-adverse finding. The apparent difference in the dose response between rats and monkeys may be due to a higher test article concentration at the local injection site in the rat. The higher range of dose concentrations administered to rats (2, 4, 10, and 16 mg/mL) versus monkeys (2, 4, and 6 mg/mL) combined with the lower CSF volume in rats may have contributed to the increased test-article related findings in rats. Further, given the technical challenges of IT injection in rats, it is possible that the increased incidence of neurologic findings may be, at least in part, due to the procedure rather than the test article alone. Therefore, in consideration of these data and its relevance to the human when considering CSF volume, the monkey is considered the more relevant model for determining toxicities. The only other toxicity observed in monkeys was the observation of decreased activity, which may have been indicative of stress and/or general malaise associated with the anesthesia and dosing procedure. This occurred in 2/8 animals at the 2-mg dose in the repeat-dose study after the second dose only. All other findings of decreased activity occurred at the 4 and 6 mg doses. Transient neurologic effects in monkeys and rats were both monitorable and reversible. Overall, these findings suggest that the nonclinical studies conducted to date have adequately characterized the safety profile of WVE-120101 to initiate the Phase 1b/2a study.

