In the single- and repeat-dose toxicity studies of WVE-120101, dose-related observations on limb dysfunction were observed in both rats and monkeys. Additional neurologic findings related to limb dysfunction were also observed in the rat which were likely related to high local concentration of test-article within a small CNS space as compared to the monkey. Furthermore, the technical complexities of IT administration to small animal models may contribute to the findings in the rat. In monkeys no findings of limb dysfunction were reported at the lowest dose (2 mg) evaluated in either the single-dose or repeat-dose studies. Application of a 10-fold safety margin to the human equivalent dose (HED), based on CSF volume, at the 2-mg dose in monkeys suggests a clinical starting dose of 2 mg. The clinical starting dose of 2 mg is also 1/13 the HED of the 0.05-mg dose in rats. Findings at this dose in rats were limited to transient, minimal clinical observations of ataxia (2 males and 3 females) after the first dose only. In addition, the dose concentration of 0.2 mg/mL that will be administered to humans is 1/10 the dose concentration administered to rats at the 0.05-mg dose (HED 28 mg) and monkeys at the 2-mg dose (HED 22.4 mg) in the repeat-dose toxicity studies.

The proposed high dose of 32 mg is expected to produce CSF exposures that are within the range of those tested and found to be well-tolerated in animals. In the 13-week monkey study, estimated peak CSF concentration at the 6 mg NOAEL dose (HED 67.2 mg) was approximately 0.48 mg/mL (based on an estimated CSF volume of 12.5 mL). In the rat, the NOAEL dose of

0.25 mg (HED 140 mg) produced an estimated peak CSF concentration of 1 mg/mL (based on an estimated CSF volume of 0.25 mL). The 32 mg dose is expected to produce a peak CSF concentration of 0.23 mg/mL, which is approximately 2-fold and 4-fold lower than those achieved in the monkey and rat, respectively, at the NOAEL-dose levels. To date, data from this study indicate that the drug has been well tolerated in patients at all dose levels evaluated. Doses of 4 mg (HED 44.8 mg) were also well-tolerated in monkeys when administered by once monthly intrathecal injection for 9 months (10 doses).

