Visit	Pre-Screening a	Screening b	Double-Blind Treatment (Single Dose)		Sentinel Patient Follow-up	Follow-up		Double-Blind Treatment (Multiple Dose)			Follow-up		
	1	2	3	4	5	6	7	8 c	9	10	11 or ET	12	13
Week		-4 to 0	0	0	0	2	4	8	12	16	20	28	30
Study Day (Visit Window, if applicable) Event/Assessment		Day -28 to -1	Day -6 to Day 1 (Baseline)	Day 2 (24 ± 4h postdose)	Day 3 (48 ± 4h postdose)	Day 14 (±2)	Day 28 (±3)	Day 56 (±3)	Day 84 (±3)	Day 112 (±3)	Day 140 or ET (±5)	Day 196 (±5)	Day 210 d (EOS) (±5)
Study drug administration via IT injection p			X					X	X	X			
Postdose on Dosing Days	-												
Physical examination e			X					X	X	X			
Adverse event monitoring			X q					X	X	X			
Clinical laboratory tests k			X					X	X	X			
Concomitant medications			X					X	X	X			
Vital signs l			X					X	X	X			
Blood samples for PK m			X							X			
Study completion													X

Abbreviations: AE = adverse event; CAG = cytosine-adenine-guanine; CSF = cerebrospinal fluid; C-SSRS = Columbia-Suicide Severity Rating Scale; ECG = electrocardiogram; EOS = end of study; ET = early termination; h = hour; HBsAg = hepatitis B surface antigen; HCV = hepatitis C virus; ICF = informed consent form; IT = intrathecal; MRI = magnetic resonance imaging; PBA-s = Short Problem Behaviors Assessment; PD = pharmacodynamics; PK = pharmacokinetics; SNP= single nucleotide polymorphism; SNP1 = SNP rs362307 T= thymine; UHDRS = Unified Huntington’s Disease Rating Scale.

Note: The UHDRS, PBA-s, and C-SSRS should be completed prior to any other assessments. Assessments completed predose on Day 1 are considered Baseline.

**\*For each dosing visit (Day 1/Visit 3 [single dose phase]; Day 56/Visit 8; Day 84/Visit 9; and Day 112/Visit 10 [multiple dose phase]), these predose procedures must be performed predose on the day of dosing. All other predose assessments (inclusion/exclusion criteria [Day 1/Visit 3 and Day 56/Visit 8 only], physical examination, UHDRS, PBA-S, clinical laboratory tests [including a blood sample to confirm platelet count and prothrombin clotting time], blood sample for PK, and blood sample for immunogenicity) may be performed up to a week prior to dosing.**

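### Stopping criterion 3 is described as covering any neurological toxicity not caught as serious or severe, but it counts one MedDRA group, so no numeric trigger is assured to count Grade 2 limb weakness, ataxia or gait change while a cohort is being dosed

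*Combined protocol and SAP*

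**What the plan says.** Section 4.3.4.1 suspends single-dose escalation on any of three criteria:

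1. One related SAE.
2. Two or more patients with a related TEAE of Grade 3 or higher.
3. Four or more patients with a related, non-serious TEAE of Grade 2 or higher in one group, the "High Level Group Term (HLGT) *Spinal cord and nerve root disorders*, assessed as related to study drug".

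The synopsis repeats criterion 3 with the same group. Its purpose is given directly below the list: it "was developed to assess any potential events of neurological toxicity that were not otherwise captured via surveillance of serious and severe TEAEs".

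Section 1.3 reports limb dysfunction in rats and monkeys and ataxia in rats. Section 2.1 calls the limb findings dose-related in both species. Section 8.2.3 points the post-dose examination at strength, tone, reflexes and ambulation. Section 9.1 has a dedicated neurological eCRF form and makes worsening on it reportable as an AE.

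On oversight, the synopsis states: "Throughout the study, unblinded aggregate safety data will be reviewed periodically and on an ad hoc basis by the SMC". Sections 4.3.1 and 4.3.3 require unblinded SMC review before escalation or multiple dosing.

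**The concern.** The stated purpose covers any neurological toxicity below the serious or severe level, while the event set is a single anatomical group. That group has a rationale, since Section 1.3 describes nerve root degeneration in rats. But no section places weakness, ataxia, gait, tone or reflex terms inside it. Table 4 lists the preferred terms that are exempt from the stopping criteria; there is no matching list of terms that count.

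The study therefore looks for these signs and records them, but no count is assured to act on them. The other triggers do not help with non-serious Grade 2 events: criterion 1 and the sentinel rule (Section 4.3.2) need an SAE, and criterion 2 needs Grade 3. At stake is whether a cluster of moderate motor signs must reach the SMC while the remaining patients of a first-in-human intrathecal cohort are still being dosed one after another.

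**Working it through.** The plan gives no operating characteristics for its stopping rules, so there is no stated figure to reproduce.

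**Inputs from the protocol.** 9 active and 3 placebo patients per cohort (Section 4.1); a threshold of 4 patients (Section 4.3.4.1).

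**Assumptions.** p is the true rate of related, non-serious Grade 2 motor events in active patients. f is the share of these that code inside the group. Neither is in the documents, so p is shown from 10% to 75% and f from 0 to 1. Events are counted within one cohort and patients are independent. The rat figure in Section 1.3 ("5/20 animals had transient ataxia after the first dose only; no events of limb dysfunction were reported") is not used to set p: Section 2.1 calls those signs transient and minimal, so the human equivalent might be Grade 1 and uncounted.

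**Step 1: chance that criterion 3 is met by these events.** P(X ≥ 4), with X ~ Binomial(9, p × f). For p = 50% and f = 1: 1 − (1 + 9 + 36 + 84)/512 = 1 − 130/512 = 0.746.

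| p | f = 0 | f = 0.5 | f = 1 |
|---|---|---|---|
| 10% | 0 | 0.06% | 0.8% |
| 25% | 0 | 2% | 17% |
| 50% | 0 | 17% | 75% |
| 75% | 0 | 45% | 99% |

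At f = 0, even 9 of 9 affected active patients would meet no group trigger. A count that covers these terms by name gives the f = 1 column whatever the coding. Adding the 3 placebo patients at an assumed 5% background rate raises the f = 1 figures only to 20% at p = 25% and 77% at p = 50%.

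**Step 2: active patients still undosed at the fourth case.** T is the position of the fourth affected active patient (negative binomial). The average over all cohorts is the sum over t = 4 to 9 of P(T = t) × (9 − t), assuming one-by-one dosing and instant detection. For p = 50%: 0.0625×5 + 0.125×4 + 0.15625×3 + 0.15625×2 + 0.1367×1 = 1.73. The results are 0.01 at p = 10%, 0.24 at 25%, 1.7 at 50% and 3.7 at 75%.

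**Step 3: unneeded reviews under an added review trigger.** b is the assumed share of all 12 patients with a listed Grade 2 event wrongly judged related. P(X ≥ 4), with X ~ Binomial(12, b), is the chance per cohort.

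| b | 5% | 10% | 15% | 20% | 25% | 30% |
|---|---|---|---|---|---|---|
| chance per cohort | 0.2% | 2.6% | 9.2% | 21% | 35% | 51% |

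If the count ran across all 60 patients instead, the chance would be 35% at b = 5% and 86% at b = 10%.

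**The case against.** The strongest reply is that only the purpose sentence is shown to be wrong. The coding hierarchy is not in the documents; if the motor terms sit inside the group, criterion 3 already counts them. This stands, and it makes the safety gap conditional.

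Oversight is also wider than the three criteria. The SMC reviews unblinded data periodically and ad hoc, and the text below Table 4 describes that review as ongoing. It may recommend stopping at any time (Section 4.3.1), and a Charter that we cannot see may set review intervals or triggers (Section 13.1). Examinations are frequent, and investigators are told to note even subtle weakness after dosing. A reader might infer that a Grade 2 cluster would go unreviewed; the documents do not support that. What remains is that nothing in the protocol makes a mid-cohort review mandatory at any number of such cases.

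Nor do the documents support the inference that neurotoxicity is expected at 32 mg. That dose lies between the monkey human-equivalent doses with no limb dysfunction (22.4 mg) and with infrequent limb dysfunction (44.8 mg). But the 13-week monkey NOAEL equates to 67.2 mg, the animal signs were transient and assessed as non-adverse, and Section 2.1 states: "To date, data from this study indicate that the drug has been well tolerated in patients at all dose levels evaluated".

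The benefit is modest, and a review without suspension does not itself stop dosing. Both points stand. The threshold of 4 is kept for consistency with criterion 3 and has not been optimised. At 3 patients, detection at p = 25% and f = 1 would be 40% instead of 17%, with unneeded reviews of 2.0% instead of 0.2% per cohort at b = 5%, and 11% instead of 2.6% at b = 10%.

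**Conclusion.** The mismatch between the stated purpose and the event set is in the current text and should be corrected. The safety gap behind it is that the protocol does not assure that Grade 2 limb weakness, ataxia, gait, tone or reflex changes count toward any numeric trigger during dosing of a cohort. Its size depends on coding. At a 50% event rate, the chance of four or more counted events runs from 75% (all coded inside) through 17% (half) to 0 (none). If all code inside, only the sentence is too broad.

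The harm is bounded. Criteria 1 and 2 apply to any non-exempt term, and the SMC must see unblinded data before escalation or multiple dosing. The averages of 0.24 undosed active patients at a 25% rate and 1.7 at 50% are upper bounds on patients spared, because they assume instant detection and the SMC must still decide to pause. All rates are assumptions, not estimates from the trial. The change is worth making because it is cheap and concerns the kind of sign seen in the animal studies. Confidence is medium.

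**What to change.** In Section 4.3.4.1 and, where it applies, the synopsis:

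1. Keep criterion 3, its group and its threshold unchanged as the suspension rule.
2. Align the purpose sentence with what is counted: related, non-serious spinal cord and nerve root events of Grade 2 or higher.
3. Add a preferred-term list in the style of Table 4: limb weakness, ataxia or coordination, gait, tone and reflex abnormalities.
4. Require prompt unblinded SMC review, without automatic suspension, when 4 or more patients in one cohort have a related, non-serious TEAE of Grade 2 or higher from the group or the list.

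The Table 4 exemptions stay. No separate rule on judging worsening is needed, since the TEAE definitions in Sections 9 and 10.9.1 largely cover it.

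The cost is one list and a few sentences in an amendment; coding, the eCRF form, examinations and the committee already exist. Because the added trigger is review-only, it avoids the all-cohort suspension in Section 4.3.5 and the regulatory submission before restart. The downside is unneeded reviews, since every patient has manifest motor HD and relatedness is judged blinded: rare at a 5% to 10% false-related rate, but 21% per cohort at 20% and 51% at 30%. Section 9.1 helps to keep that rate low, because worsening seen only on rating scales is not an AE. The count should be limited to one cohort, for the reason shown in Step 3.
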